Research proposal

1. Project title

The effects of different inspiratory pressures on the diaphragmatic thickness fraction and sternocleidomastoid muscle activation in people after stroke

2. Abstract

This study is a cross-sectional study to determine the optimal inspiratory muscle training (IMT) intensity for stroke survivors. Participants will breathe through a pressure threshold inspiratory loading device with varying loads in random order. During the test, accessory inspiratory muscle (sternocleidomastoid muscles) activity will be measured with surface electromyography (sEMG) and diaphragm thickness will be used to assessed with ultrasonography. Repeated-measures ANOVA will be used for statistical analysis to determine the most effective training intensity.

3. Project objectives

Introduction:

Stroke was the second largest cause of global death and disability in 2019 [1]. Direct medical costs for stroke in China was 50 billion yuan (nearly 7.69 billion US dollars) in 2015, and this accounted for the highest medical cost in China [2]. In 2016, the Global Burden of Disease (GBD) study estimated that the lifetime risk of stroke from the age of 25 years was 39.3% in China, which is the highest estimated risk in the world [3]. In 2018, stroke was the third highest disease cause of death, accounting for 1.57 million deaths in China [4].

Stroke not only causes impairment of motor function but can also affect lung function [5]. The lung function (e.g. forced vital capacity (FVC), forced expiratory volume in one second (FEV1), maximal inspiratory pressure (MIP), peak expiratory flow (PEF)) in people after stroke was reported significantly lower than the age and gender-matched healthy adults [6, 7]. Impaired lung function in people after stroke not only leads to high risk of pneumonia, poor functional outcomes and prolonged hospitalization but may also increase mortality [8-10].

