Inspiratory muscle training (IMT) is an intervention designed for improvement of inspiratory muscle (including the diaphragm) strength and endurance in healthy adults and patients suffering from different diseases (e.g. Parkinson, chronic obstructive pulmonary disease, cardiovascular disease) [18-21]. Regarding the IMT training protocol, the commonly reported training intensities varied between 30-80% of MIP in people after stroke [22-24]. Although the diaphragm is the primary inspiratory muscle, the use of IMT may not help improve the diaphragmatic contraction under some circumstances. Previous studies suggested that, in healthy adults and people receiving mechanical ventilation, when inspiratory load exceeds the capacity of the diaphragm (higher than 60% MIP), the accessory respiratory muscle (in particular the sternocleidomastoid muscle) would be activated dramatically, which would increase work of breathing and fatigue [25, 26]. Other studies also reported that high IMT intensity may have the risk to increase the work of breathing thereby leading to fatigue [27] or resulting in a decrease, rather than increase, in surface electromyography signals in diaphragmatic activity [27]. It is postulated that IMT recruits accessory muscles such as sternocleidomastoid rather than diaphragm during the practice [24]. Hence, evaluation of effectiveness of IMT on DTF in people after stroke and further investigation on determining an optimal training protocol including inspiratory effort and training intensity for recruiting diaphragmatic activities in the stroke population are warranted.

Aims of the study:

To determine the optimal training intensity that is associated with the strongest diaphragmic thickening fraction in people after stroke.

Project significance:

Outcomes of this project study will fill the existing knowledge gaps in the understanding of the relationship between inspiratory pressure and recruitment of diaphragmatic muscles in people after sub-acute and chronic stroke.

4. Research methodology

Study design:

This study will be a cross-sectional study.

Participants:

Individuals who have had a stroke and healthy adults will be invited to participate in this study.

Participants recruitment for people after stroke:

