The inclusion criteria are: (1) age \geq 18 years; (2) clinically diagnosed with ischemic and/or hemorrhagic stroke; (3) duration of stroke range from 1 month to 12 months after diagnosis; (4) had no facial palsy, which could prevent proper labial occlusion; (5) had not undergone thoracic or abdominal surgery; (6) could understand and follow the verbal instruction; (7) stable cardiac conditions; (8) no previous history of respiratory problems.

The exclusion criteria are: (1) acute myocardial infarction or acute heart failure; (2) acute pain on chest or abdominal; (3) with the clinical signs of significant pulmonary disease; (4) consciousness impaired; (5) patient with nasal feeding tube, tracheal tube and/or any condition, which prevent the measurement or training.

Recruitment of healthy participants:

The inclusion criteria are: (1) age ≥ 18 years; (2) had not undergone thoracic or abdominal surgery; (3) no previous history of respiratory problems.

The exclusion criteria are: (1) acute myocardial infarction or acute heart failure; (2) acute pain in the chest or abdominal; (3) with the clinical signs of significant pulmonary disease; (4) unstable hypertension, arrhythmias, or unstable cardiovascular conditions, such as fluctuations in blood pressure and heart rate, indicate poor cardiac prognosis or the need for vasopressor medications; (5) pregnant.

Ethical approval:

Ethical approval will be sought from the Research Ethics Committee of Hong Kong Metropolitan University and Shenzhen Second People's Hospital.

Sample size calculation:

Sample size calculation will be based on the use of repeated-measures analysis of variance (ANOVA) using the G*Power 3.1. Considering an effect size of 0.2, an alpha error probability of 0.05 and a power of 0.80, the estimated sample size is 54 participants. An additional 20% of the sample size will be included to account for attrition. The final estimated sample size will be at least 130 participants (65 for each cohort).

Procedure:

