After the baseline measurement, all participants will be requested to use a nose clip to hold the nose and breathe with the mouth through a pressure threshold inspiratory loading device (POWERbreathe, KH2, England). The inspiratory pressure will be set at 30%, 40%, 50%, 60%, 70%, or 80% of their MIP, in random order. Each MIP intensity protocol consists of 10 breaths. The procedure of IMT is followed by the published research protocols in people after stroke [28]. All MIP intensity protocols will be conducted in one day. A period of at least 10 minutes of rest time will be allowed between different protocols of contraction intensity (% MIP) on the same day [29].

Thickness of the left and right diaphragm (stroke and non-stroke), will be measured simultaneously by two identical ultrasonography at the end of maximum inspiration of 10 breaths of each MIP intensity protocol. The diaphragm thickness of both the left and right diaphragm at the end inspiratory breaths of the 10 breaths of each MIP intensity protocol will be recorded. Surface electromyography (sEMG) will be used to measure the activity of accessory muscle (sternocleidomastoid muscles) during each MIP intensity protocol. The % of MIP that associates with the highest calculated DTF and a relatively stable change in the activity of accessory muscles will be considered an appropriate training intensity for further IMT protocols.

The self-perceived exertion level will also be determined by the Rate of Perceived Exertion Borg scale at the end of each MIP intensity protocol [30].

All research procedures will be repeated again after 2 days to examine the test-retest reliability of ultrasonographic measurements of DTF.

Outcome measures:

[figure not shown]
Lung function

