Though various measures will be taken to minimize the risk of adverse event throughout the study, any adverse events that might happen will be recorded.

Statistical analysis:

All data will be reported as mean \pm standard deviation (SD) unless otherwise indicated. Demographic data and clinical characteristics for all participants will be summarized using descriptive statistics. Repeated-measures ANOVA will be used to compare the differences of DTF and sEMG parameters determined at each inspiratory pressure separately. Intraclass correlation coefficient will be used to determine the inter-rater reliability of two ultrasonic operators and examine the test-retest reliability coefficient of ultrasonographic measurements of DTF recorded with different inspiratory pressures.

P value will be set at 0.05. All data will be analyzed using the IBM SPSS Statistics for Windows, Version 25.0 (Armonk, NY: IBM Corp).

References:

1. Gbd, S., Global, regional, and national burden of stroke and its risk factors, 1990-2019: a systematic analysis for the Global Burden of Disease Study 2019. *Lancet Neurol*, 2021. 20(10): p. 795-820.
2. Wu, X., et al., The hospital costs of stroke patients in Chinese island populations: an 11-year tendency analysis. *J Stroke Cerebrovasc Dis*, 2015. 24(5): p. 988-992.
3. Feigin, V., et al., Global, Regional, and Country-Specific Lifetime Risks of Stroke, 1990 and 2016. *N Engl J Med*, 2018. 379(25): p. 2429-2437.
4. Li X and Z. X., Annual data set on national mortality surveillance 2018. Beijing: China Science and Technology Press, 2019.
5. Menezes, K.K., et al., Respiratory muscle training increases respiratory muscle strength and reduces respiratory complications after stroke: a systematic review. *J PHYSIOTHER*, 2016. 62(3): p. 138-44.
6. Liu, X., et al., Assessment of Diaphragm in Hemiplegic Patients after Stroke with Ultrasound and Its Correlation of Extremity Motor and Balance Function. *Brain Sciences*, 2022. 12(7): p. 882.
7. Lista-Paz, A., et al., Pulmonary function in patients with chronic stroke compared with a control group of healthy people matched by age and sex. *Physiother Theory Pract*, 2022: p. 1-9.
8. Wilson, R., Mortality and cost of pneumonia after stroke for different risk groups. *J Stroke Cerebrovasc Dis*, 2012. 21(1): p. 61-67.
9. Saposnik, G., et al., Variables associated with 7-day, 30-day, and 1-year fatality after ischemic stroke. *Stroke*, 2008. 39(8): p. 2318-2324.

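### The rule for choosing a training load has no outcome for a DTF maximum at 30% or 80% MIP and uses no load-order information, so an end-of-range or chance maximum could be reported as the optimum

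*Combined protocol and SAP*

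**What the plan says.** The aim (section 3, Aims of the study) is "To determine the optimal training intensity that is associated with the strongest diaphragmic thickening fraction in people after stroke". The Abstract expects the ANOVA to deliver it: "Repeated-measures ANOVA will be used for statistical analysis to determine the most effective training intensity".

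The loads are six equally spaced steps (section 4, Procedure): "The inspiratory pressure will be set at 30%, 40%, 50%, 60%, 70%, or 80% of their MIP, in random order". The Introduction gives the background for the range: "the commonly reported training intensities varied between 30-80% of MIP in people after stroke".

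The selection rule in the Procedure has two joint parts. The first concerns the diaphragm: "The % of MIP that associates with the highest calculated DTF". The second, in the same sentence, concerns the sternocleidomastoid electromyography: "and a relatively stable change in the activity of accessory muscles will be considered an appropriate training intensity for further IMT protocols".

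The Statistical analysis section states: "Repeated-measures ANOVA will be used to compare the differences of DTF and sEMG parameters determined at each inspiratory pressure separately". It names no trend contrast, dose-response model, pairwise comparison or interval for the chosen load. No section says what to report if the highest DTF lies at 30% or 80% MIP.

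**The concern.** Whether DTF rises and then falls with load, or only rises or only falls, is a question about the shape of a curve over an ordered scale. The planned ANOVA treats the loads as six labels. It can show that they differ, but not whether there is a turning point.

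The selection step does not supply the missing information. Among six values there is always a highest, so the DTF part cannot return a finding that no peak was seen. If DTF is still rising at 80%, or is falling from 30%, the data show the best load tested and nothing about what lies beyond. If the curve is nearly level at the top, chance decides which load comes first. The rule treats these cases and a true interior peak alike, and its result is meant to feed later training protocols.

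**Working it through.** **Inputs from the documents.** Six loads, 30% to 80% MIP in steps of 10 (Procedure). From Sample size calculation: "Considering an effect size of 0.2, an alpha error probability of 0.05 and a power of 0.80, the estimated sample size is 54 participants". With 20% added, this is 54 × 1.2 = 64.8, or 65 per cohort.

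**Assumptions, because the documents do not give them.** The effect size is Cohen's f. The correlation between loads is rho, with equal variances and correlations (epsilon = 1). DTF is compared as group means; the text does not say whether it means group means, individuals or one side. The electromyography condition is left out because it has no definition that could be simulated.

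**The plan's own figure.** lambda = f² × N × m × epsilon / (1 − rho), with df1 = (m − 1) × epsilon and df2 = (N − 1)(m − 1) × epsilon. For m = 6 and f = 0.2:
- rho = 0, epsilon = 1: N = 55.
- rho = 0.2, epsilon = 0.75: N = 54.
- rho = 0.5, epsilon = 1: N = 28.

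So 54 is attainable but not fixed by the stated inputs. I therefore use two effect sizes at N = 54:
- Effect sized for 80% power on 5 and 265 df: lambda = 13.10.
- f = 0.2, rho = 0.5: lambda = 0.04 × 54 × 6 / 0.5 = 25.92.

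**Straight rising curve, by hand.** In within-person SD units, N × sum(mu²) = lambda. For equal steps d, sum(mu²) = 17.5 d². The standard error of a difference between two means is sqrt(2/54) = 0.1925.
- lambda = 13.10: d = sqrt(13.10 / 54 / 17.5) = 0.118, or 0.61 standard errors. The 70% mean exceeds the 80% mean with probability 0.27.
- lambda = 25.92: d = sqrt(25.92 / 54 / 17.5) = 0.166, or 0.86 standard errors; probability 0.19.

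**Simulation of the highest mean (20,000 trials per curve).**

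| True curve | lambda 13.10 | lambda 25.92 |
|---|---|---|
| Straight rise: 80% highest | 68% | 79% |
| Straight rise: interior load highest | 32% | 21% |
| Same, among trials with a significant ANOVA | 31% | 21% |
| Plateau from 60%: interior load highest | 68% | 67% |

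A straight fall mirrors the rise. With 65 rather than 54 completers, at f = 0.2 and rho = 0.5, the interior share for a rise is 18%.

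**What a trend test adds.** At lambda = 13.10, a 2-df linear-plus-quadratic test has power 0.907 if the curve lies wholly in those two terms, and 0.88 to 0.91 for the rising, plateau and peaked curves tried, against 0.80 for the 5-df test.

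**What would justify claiming a peak.** Two conditions were compared, each also requiring the highest mean at 40–70%: (A) a negative quadratic contrast, one-sided 2.5%; (B) the top load exceeds both the 30% and 80% loads in paired t tests, Bonferroni over two. Each range runs from lambda 13.10 to 25.92.

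| True curve | A declares a peak | B declares a peak |
|---|---|---|
| Straight rise | about 2% | 0.1–0.2% |
| Plateau from 60% (no peak) | 22–37% | about 2% |
| Quadratic peak at 60% | 83–98% | 28–48% |
| Quadratic peak at 70% | 33–52% | 3–4% |

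Condition A detects flattening, which is not a downturn. Condition B protects against a false peak but confirms a real one less often. Without the Bonferroni adjustment, B confirms the 60% peak in 40–62% of trials and passes the plateau in about 4–5%.

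**The case against.** Four points can be made for the plan.

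**The load is not chosen on DTF alone.** A reader who stops at the first half of the rule might infer that it is. The rule also requires a relatively stable change in accessory muscle activity. The Introduction reports, from healthy adults and ventilated patients, that sternocleidomastoid activity rises sharply above 60% MIP, so this condition might block a maximum at 80%. That stands, and the percentages above describe only the DTF part. But the condition has no threshold and no rule for when the two parts disagree. It would not obviously block a maximum at 30%, and it cannot show whether DTF turned down.

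**The plan does not promise a turning point.** A reader might infer that an end-of-range maximum would certainly be announced as a peak. The documents do not say so. The aim speaks of the strongest DTF, and the Procedure calls the selected load appropriate. The highest DTF among loads in the commonly used range is a legitimate, interpretable result. What remains is that the aim and Abstract call the result optimal or most effective, and nothing limits that claim.

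**A flat curve.** A reader might infer that a flat curve yields a false interior optimum in two thirds of trials, since four of the six loads are interior. That holds only if a load is named whatever the ANOVA shows. If a significant ANOVA is needed first, the figure is about 5% × two thirds, or 3%. No such condition is written, but the Abstract makes it a natural reading. For a straight rising curve, conditioning on significance barely changes the result.

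**Trend contrasts are partly a design preference.** True. The power gain applies to the curves tried, and the case for change does not rest on it.

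**Conclusion.** The point holds as a cheap improvement. The plan uses no load-order information, the DTF part of the rule always returns a load, the electromyography part is undefined, and no outcome is provided for a maximum at 30% or 80% MIP. These four facts come from the text and need no assumptions.

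The size does need assumptions. For a straight rising curve with 54 completers, the highest mean lies at an interior load in about 21% of trials (f = 0.2, rho = 0.5) to 32% (effect sized for 80% power). In the remaining 68–79% it lies at 80%, where the data cannot show a maximum. These figures take the DTF part alone, applied to group means.

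The documents do not support saying that the trial will report a false optimum, nor that a significant quadratic contrast by itself would settle the matter.

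**What to change.** In the Statistical analysis section, add planned linear and quadratic contrasts of DTF across the six loads alongside the ANOVA. Report paired differences, with confidence intervals, between the load with the highest mean DTF and each of the 30% and 80% loads, and state any multiplicity adjustment.

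In the Procedure, state that a peak within the range is claimed only if the highest mean is at an interior load and that load exceeds both end loads in these comparisons. Otherwise report *highest DTF among the loads tested; no peak shown within 30–80% MIP*, with the direction of the trend. Also define the accessory-muscle condition, and say whether highest DTF refers to group means and to which side.

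The cost is a few sentences and a standard SPSS contrast option, with no new data. The downside is real: under the assumptions above, a quadratic peak at 60% is confirmed in only about 30–50% of trials and one at 70% in about 3%, so the trial may have to report that no peak was shown. The sponsor should accept or adjust that trade-off before data are seen. No load is proposed here as clinically right.

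### The optimal load is assigned to repeated-measures ANOVA, whose overall F test does not by itself identify it, and no between-load comparison or interval accompanies the load chosen by highest DTF

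*Combined protocol and SAP*

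**What the plan says.** The document states its goal in three places and its analysis in one.

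- Abstract: the study is "to determine the optimal inspiratory muscle training (IMT) intensity for stroke survivors", and "Repeated-measures ANOVA will be used for statistical analysis to determine the most effective training intensity".
- Section 3, Aims of the study: "To determine the optimal training intensity that is associated with the strongest diaphragmic thickening fraction in people after stroke".
- Section 4, Procedure: "The inspiratory pressure will be set at 30%, 40%, 50%, 60%, 70%, or 80% of their MIP, in random order". The load with the "highest calculated DTF and a relatively stable change in the activity of accessory muscles will be considered an appropriate training intensity" is to be carried into later IMT protocols.
- Section 4, Statistical analysis: "Repeated-measures ANOVA will be used to compare the differences of DTF and sEMG parameters determined at each inspiratory pressure separately", and "P value will be set at 0.05".

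Apart from the ANOVA, the Statistical analysis section names means with SDs, descriptive summaries, and intraclass correlations for reliability. It names no planned contrast or post hoc test between loads, no multiplicity adjustment and no confidence interval. Neither section says how relatively stable accessory-muscle activity is to be measured, or which side's DTF decides when left and right are both recorded. The Sample size calculation section sizes the study for the ANOVA: "Considering an effect size of 0.2, an alpha error probability of 0.05 and a power of 0.80, the estimated sample size is 54 participants", raised by 20% to 65 per cohort.

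**The concern.** The question asked is which load is best. The overall F test answers another one: whether the six means differ at all. A significant F is compatible with one load standing apart, with a gentle peak whose neighbours are almost as good, or with several loads tied at the top.

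The chosen %MIP is the study's main product. As written, the report could give a significant F next to the highest observed mean and present that load as the optimum, with nothing to show whether the data separate it from adjacent loads.

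**Working it through.** **Inputs from the document.** Six loads, hence 6 × 5 / 2 = 15 pairs per outcome; effect size 0.2; alpha 0.05; power 0.80; base n = 54; 65 per cohort.

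**Assumptions not in the document.** The 0.2 is Cohen's f; sphericity; equal correlation rho between loads of 0, 0.5 or 0.8; three shapes for the true DTF curve. The sEMG condition is not modelled.

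**1. The plan's own figure.** For a within-person factor with m = 6, noncentrality is f² × n × m / (1 − rho), with 5 and 5(n − 1) degrees of freedom. At rho = 0 and n = 54 this is 0.04 × 54 × 6 = 12.96, giving power 0.795; n = 55 gives 0.804. So 54 is close to this setting. Other unstated settings also reach it (rho = 0.2 with a non-sphericity factor of 0.75 gives 54), while rho = 0.5 under sphericity gives 28. The 54 therefore cannot be tied to one set of inputs. The later step does reproduce: 54 × 1.2 = 64.8, rounded to 65, and 2 × 65 = 130.

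**2. How often F is significant at n = 54.** Noncentrality is 12.96 / 25.92 / 64.8 for rho = 0 / 0.5 / 0.8. Power is 0.80 / 0.99 / 1.00, whatever the shape of the curve.

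**3. How often the highest mean is the wrong load.** Each shape is scaled so that the SD of the six true means is 0.2 (in units of the within-load SD). Comparisons between loads depend on an error SD per mean of √((1 − rho)/n). Simulated results at n = 54, rho = 0 / 0.5 / 0.8:

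| True shape | Gap, best to next (SD) | Highest mean is not the best load | Expected DTF loss (SD) |
|---|---|---|---|
| Smooth interior peak | 0.07 | 54 / 46 / 34% | 0.04 / 0.03 / 0.02 |
| Linear rise | 0.12 | 32 / 21 / 9% | 0.05 / 0.03 / 0.01 |
| One load alone | 0.54 | about 1 / 0 / 0% | under 0.01 |

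At n = 65 the smooth peak gives 52 / 44 / 31% and the linear rise 29 / 19 / 7%.

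**4. What it takes to separate two loads.** The margin is the critical value × √(2(1 − rho)/n). At n = 54 the square root is 0.192 / 0.136 / 0.086.

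- Bonferroni over 15 pairs, two-sided (2.962): 0.57 / 0.40 / 0.25 SD.
- Dunnett-type, one-sided (2.247): 0.43 / 0.31 / 0.19 SD.

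A best-to-next gap of 0.07 or 0.12 SD lies below every one of these margins. A gap of 0.54 SD exceeds all but the Bonferroni margin at rho = 0. Whether a single load can be claimed thus depends on the shape of the curve, which F does not show.

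**5. Why the follow-up method must be named.** With no true differences, rho = 0.5 and n = 54, unadjusted testing of all 15 pairs gives at least one significant pair in about 37–38% of simulated studies. Leaving the choice open would leave the conclusion open.

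**The case against.** The strongest reply is that the Procedure does not choose a load by significance test. It gives a selection rule for an appropriate intensity, which is softer wording than an optimum, and taking the largest mean is a legitimate way to select. This stands. A reader might infer that the plan cannot name or support any load, but the document does not bear that out: the rule yields a point estimate, and what is missing is a statement of its uncertainty. The reply does not cover the abstract and the aim, which do promise the most effective or optimal load and, in the abstract, assign it to the ANOVA.

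A second reply is that the practical loss is small and the error rates rest on assumptions. Both parts stand. The wrong-load rate runs from 0 to 54% across the assumed shapes and correlations, so it does not size the problem in this study. The highest figures use rho = 0, which takes six same-day measurements on one person to be uncorrelated. The point that F does not identify the best load needs none of these assumptions.

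A third reply is that post hoc tests are implied, perhaps by the word separately in the Statistical analysis section. That word most naturally means that DTF and sEMG are analysed apart; it specifies no pairwise test.

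**Conclusion.** The point holds in a limited form and should be fixed. The overall F test does not by itself identify the best load, and the load picked by highest DTF comes with no between-load comparison or interval.

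The illustrative rates depend on f = 0.2, sphericity, the assumed rho and the curve shape. Across them the expected DTF loss is at most about 0.05 SD (linear rise, rho = 0, n = 54). The harm is therefore an unsupported claim of one optimum, not a large loss of effect.

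Two stronger conclusions should not be drawn. It does not follow that the chosen load will probably be wrong: if one load stands alone, the highest mean finds it in about 99% of studies or more. Nor is any planned figure shown to be wrong, since the defect is an omission in the analysis.

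**What to change.** - **Statistical analysis.** Keep the F test. Add, for the stroke cohort, comparisons of mean DTF between loads by one pre-named method that gives simultaneous 95% intervals: for example Bonferroni-adjusted pairwise differences, or a Dunnett-type comparison with the best. If Holm is preferred, drop the simultaneous-interval requirement, because Holm has no simple matching intervals.
- **Procedure.** Report the highest-DTF load together with the set of loads not shown to be lower. Claim a single optimum on DTF only if that load is separated from all the others; otherwise report the range.
- **Abstract.** Reword so that ANOVA alone is not said to determine the most effective intensity.
- **As part of the same change, before data are seen.** State which side's DTF decides, how relatively stable sEMG is measured, and how it is combined with the DTF set. Without this the two-part rule cannot be carried out.

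Possible wording: *In the stroke cohort, differences in mean DTF between loads will be assessed by [one named method] at a familywise level of 0.05, with simultaneous 95% intervals. The loads not shown to have lower DTF than the highest will be listed, and a single optimum on DTF will be claimed only if one load remains.*

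The cost is wording in three sections and a short extra analysis of data already planned. No extra participants are needed to report a range. The downside is that the DTF result will often be a range of loads.
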